6. * Since a separate protocol document is not uploaded, describe the proposed research using language understandable to those IRB committee members whose expertise is not scientific. The description must include:

1. A statement explaining the study design

2. A detailed description of all the procedures that will be followed to carry out the study, preferably in sequential order, and in sufficient detail that the study's methods could be replicated

3. A description of all research measures/tests/interventions that will be used (if applicable)

See the help text for additional guidance

1.

Randomized Controlled Trial.

The biostatistician on the study team ([name]) will generate random sequence in blocks of 4 using a computer.

All study participants will be assigned a unique identifier (4 digit code) generated by the study team based on order of enrollment and the type of attachment. The key that links code to the patient will be stored in the PI's office computer that has restricted access (only to study personnel). The key will be destroyed when the study is completed.

2.

Members of the study team including residents, [name] will have a meeting prior to start of the study to calibrate on the screening criteria to determine eligibility as well as obtaining signatures and maintaining the consent documents. The team will also have a virtual meeting over zoom at least once a month to update on study progress.

All members of the study team will inform [name] when a study participant is recruited to the study through a secure email. [name] will then communicate the randomly assigned attachment design to the treating orthodontist based on the sequence generated by [name]. The treating orthodontist will then put this information as an order to Align Technology for the fabrication of the attachment trays and clear aligners.

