During the scheduled appointment for the delivery of aligners, the patients will be instructed on how to properly place and remove aligners and their maintenance. Patients will be instructed to wear each aligner for a minimum of 22 hours a day for 7 days. Participants will verbally confirm compliance at each appointment. At the end of a series of 20-25 aligners, another intraoral scan will be taken and sent to Align Technologies to determine the final positions of the teeth. Comparison of initial and final positions (using Geomagic software) will be done to assess the efficacy of different types of attachments in lateral incisor extrusion.

Once the teeth are in desired positions, the treating orthodontist will remove the attachment (<6 months).

3.

Research related interventions include:

- a. random assignment of the specific type of attachment on lateral incisor;
- b. treating orthodontist placing the corresponding order in the prescription with Align Technology;
- c. delivery of attachments and aligners to the study participants
- d. Superimposition of final and initial positions of lateral incisors: Two superimpositions will be completed. The pretreatment model will be superimposed with the predicted final model to establish the predicted movement of the maxillary lateral incisors. The pretreatment model will be superimposed with the posttreatment model to establish the actual movement of the maxillary lateral incisor. The actual and predicted movement values will be calculated by the GeoMagic software. The amount of extrusion for the lateral incisors will be analyzed in increments of 0.1 mm.

Sample size: 80 maxillary lateral incisors with at least 20 teeth per study group. Randomization will occur at the level of individual lateral incisor tooth.

Study Duration: Patients will be evaluated only after the first series of aligners (20-25). Each set of aligners would be worn for a week and the study would span 20 - 25 weeks.

7. * The IRB only reviews research activities, so indicate which of the study activities are:

- **Being performed exclusively for research purposes (i.e. they would not otherwise be done apart from this study) VERSUS.**
- **Alterations of routine activities/procedures (e.g. the study is altering the timing, frequency, method, location, amount, etc.) VERSUS.**

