- **Being done for other purposes and whose data/results will be used secondarily in the study (e.g. standard medical or psychological tests, routine education practices, quality improvement initiatives, etc.).**

Research related interventions include:

- a. random assignment of the specific type of attachment on lateral incisor;
- b. treating orthodontist placing the corresponding order in the prescription with Align Technology;
- c. delivery of attachments and aligners to the study participants
- d. Superimposition of final and initial positions of lateral incisors: Two superimpositions will be completed. The pretreatment model will be superimposed with the predicted final model to establish the predicted movement of the maxillary lateral incisors. The pretreatment model will be superimposed with the posttreatment model to establish the actual movement of the maxillary lateral incisor. The actual and predicted movement values will be calculated by the GeoMagic software. The amount of extrusion for the lateral incisors will be analyzed in increments of 0.1 mm.

In clinical practice (as in this study) it is nearly always needed to take an intraoral scan at the end of the first set of aligners. This is an optical scanning of the mouth and has no additional risks associated with it. In this study, the scan will be used to assess the results of the randomized intervention. For practice purposes, it is used to construct retainers (if the treatment is done) or, more commonly, to construct an additional set of aligners to continue treatment and improve the result for the patient.

8. If applicable, describe alternatives (research or non-research) that are available to potential participants if they choose not to participate in this study:

They can choose to continue to receive the Invisalign care without being a part of the study. They will not be randomized and the treating orthodontist will choose the type of attachment based on clinical judgment and experience.

9. Upload any supporting tables or documents (e.g. protocol documents, figures/tables, data collection forms, study communications/reminders):

Upload ALL instruments/guides that will be used or that participants will experience (i.e. see, hear, complete), including measures, scripts/questions to guide interviews, surveys, questionnaires, observational guides, etc.:

Upload ALL recruitment and screening materials, including such as ads, flyers, telephone or in-person scripts,

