- Secondary data/specimens NOT from a research registry or repository
- Information/specimens from a research registry or repository (Usage Protocol)
- Information/specimens originally collected for a previous research study

- Publicly available information/specimens
- Government-generated or collected information that was or will be obtained for nonresearch activities [only applicable to research conducted by or on behalf of a Federal department or agency]
- No secondary data/specimens will be used

ID: HM20021396

View: SF2 - Secondary Data/Specimen Details

Secondary Data/Specimen Details

1. * Describe the source(s) and nature of the information/specimens being obtained. This response should:

- a. Identify where the data/specimens will come from (e.g., another researcher's registry, pathology lab, commercial source, medical records, etc.); and
- b. List what types of specimens will be obtained (when applicable); and/or
- c. List all data elements that will be obtained (when applicable). A data collection form or other documentation may be uploaded and referenced here.

1. Patient demographic information (age, sex and race) will be collected from the EHR.

2. The initial consultation appointment will include documentation of patient's clinical condition, orthodontic diagnosis & treatment plan as well as patient expectations. These are routinely entered as part of clinical notes in the EHR.

3. Intraoral scans using an optical scanner will be done at 2 time points: at the start to determine study eligibility (required lateral incisor extrusion >0.3mm and crowding <6mm) and at the end of first series of aligners (5-6 months after start of treatment) to determine the final positions of lateral incisors. The digital model of the maxillary and mandibular teeth will be stored in password-protected file. This file will be de-identified before analysis.

2. * Describe whether any agreement exists between you and data/specimen provider that states you will never have access to the ability to identify the participants (i.e. access to identifiers or the code key) and that you will not attempt to re-identify individuals.

there is no agreement between us and the data provider

3. * When the information/specimens were originally collected, did individuals provide consent for secondary research use of their data/specimens (i.e. consent to another research study or to a research registry)?

Yes

No

ID: HM20021396

View: SF2 - Costs to Participants

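### The primary outcome is measured without masking: nothing requires attachments to be off at the outcome scan, and the participant code is built from the arm

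*Combined protocol and SAP*

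**What the plan says.** Study Procedures, question 6, item 2 sets the outcome scan: "At the end of a series of 20-25 aligners, another intraoral scan will be taken and sent to Align Technologies to determine the final positions". Item 3 adds: "Each set of aligners would be worn for a week and the study would span 20 - 25 weeks". Secondary Data/Specimen Details, question 1, times the same scan "at the end of first series of aligners (5-6 months after start of treatment) to determine the final positions of lateral incisors".

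Attachment removal is a separate sentence in item 2, after the scan and the GeoMagic comparison: "Once the teeth are in desired positions, the treating orthodontist will remove the attachment (<6 months".

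Measurement is described in item 3d: "The pretreatment model will be superimposed with the posttreatment model to establish the actual movement of the maxillary lateral incisor". A second superimposition, of the pretreatment model on the predicted final model, gives the predicted movement. Extrusion is analysed in 0.1 mm steps. No registration area, landmark, treatment of the attachment or masked measurer is given.

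Question 7 says of the end-of-series scan that in practice "it is used to construct retainers (if the treatment is done) or, more commonly, to construct an additional set of aligners".

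Question 6, item 1, and Data Confidentiality and Storage, question 9, build the participant code from enrolment order and attachment type. Question 9 also puts that code on every record used for analysis.

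**The concern.** Because the arms differ only in the shape bonded to the tooth, a post-treatment model scanned with the attachment on shows the allocation on screen. Superimposition normally leaves the operator some choices, such as which region to match and whether to accept or repeat a fit, and the plan fixes none of them. Someone who can see the arm and expects one design to do better could shift the result without meaning to. Such expectations exist: Background, question 1, reports strong design preferences among both orthodontists and general dentists, although for different designs.

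The primary comparison of extrusion is at stake, and so is the secondary objective on predicted three-dimensional position, which uses the same models. If attachments come off only on teeth that have reached their planned position, the conditions of measurement would also vary with the outcome.

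**Working it through.** **1. Is the attachment on at the scan?** The passages pull in both directions.
- Suggesting it is on: the text gives the scan first and removal after it, and the form asks for "A detailed description of all the procedures that will be followed to carry out the study, preferably in sequential order". The scan is used "more commonly, to construct an additional set of aligners to continue treatment and improve the result for the patient". Background, question 1, cites 70% to 80% of aligner patients needing intervention or refinement, and 29.6% accuracy for extrusion.
- Suggesting it may be off: sequential order is only preferred. Consent Groups, question 9, and Waiver of Documentation of Consent, question 2, place incisor correction at the start of treatment.
- Stated times: 20 × 7 / 30.4375 = 4.6 months and 25 × 7 / 30.4375 = 5.7 months. This window lies inside the under-6-months limit for removal, so removal before, at or after the scan all fit.

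Attachment presence is therefore a plausible inference for many teeth, not a stated fact.

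**2. Does the code reveal the arm?** Yes, to anyone who knows the scheme. This does not depend on step 1.

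**3. Could the attachment shape itself distort the measurement?** This can be checked only on assumed dimensions.
- Whole-crown best fit, simulated with a 4 × 2 × 1 mm attachment on an ellipsoid crown: vertical shift between -0.007 and +0.006 mm.
- Crown-centroid measure, with a shelf of about 4 mm² displaced 1 mm on a crown of about 150 mm²: 4 × 1 / 150 = 0.027 mm, or about 0.05 mm between the two bevelled designs.

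Both are below the 0.1 mm increment, and the documents name neither method.

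**4. What would an operator shift do to the test?** The plan has no figure on this point. Its sample-size inputs (Study Population, question 3) do reproduce: 0.114 / (1.25² × 0.5) = 0.146, which gives 80.0% power at n = 20 under the stated repeated-measures model.

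Now suppose no true difference and a false offset b, in mm, in one arm of four. The variance of the means is V = 3b²/16. With independent groups of 20, λ = 80V/SD² on 3 and 76 degrees of freedom, tested at 0.05. For b = 0.1, V = 0.001875 and λ = 80 × 0.001875 / 1.5625 = 0.096.

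| SD | b = 0.05 | b = 0.1 | b = 0.2 | b = 0.3 |
|---|---|---|---|---|
| 1.25 (plan, taken as mm) | 5.1% | 5.5% | 7.2% | 10.3% |
| 0.5 (assumed) | 5.8% | 8.6% | 21.5% | 45.1% |

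Under the plan's repeated-measures model (SD 1.25, correlation 0.5), the rates for 0.1, 0.2 and 0.3 mm are 6.1%, 9.6% and 16.2%. The bias in that arm's contrasts with the others equals b whatever the SD. No value of b comes from the documents.

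**The case against.** A reader might infer that the outcome scan is definitely taken before removal, so that every measured model shows the arm. The documents do not support this. No sentence gives attachment status at the scan, and step 1 shows that the stated times settle nothing. The remark about further aligners describes what the scan is used for in practice. It does not say that the lateral-incisor attachment stays on.

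A reader might also infer that an arm-specific shape sits on the measured surface and biases the result. No surface or landmark is named, and the geometric estimates fall below the analysis increment.

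Nor should the threat be sized by setting a 0.05 mm operator shift against 0.3 × 0.296 = 0.089 mm of movement. The shift has no source. The 0.089 mm is a floor: it combines the minimum entry value with an accuracy figure that the same section says more recent studies have improved on.

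Preferences do not point one way either. Orthodontists most often chose the gingival bevel (46%), while general dentists chose it 3% of the time and favoured optimized attachments (50%). The measurer is not identified.

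A sponsor could add that the software calculates the movement and that the scan file is de-identified before analysis. Neither amounts to masking: the registration choices are unspecified, and the code that replaces the name is itself built from the arm.

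These objections remove the claims of certainty and of size. The absence of any masking step remains.

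**Conclusion.** The point holds as an unmasked-measurement concern and is worth fixing, but it is not a demonstrated bias. Three things are established: the plan does not require attachments to be off at the outcome scan, it describes no masking or attachment handling in the superimposition, and it builds the code on all analysis records from the arm. That many models will show the attachment is likely but inferred.

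The size is unknown. At the plan's SD, an offset of 0.1 mm barely moves the type I error. It matters more if the true SD is smaller or the offset larger. These rates assume independent teeth, 20 per arm and an offset confined to one arm.

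**What to change.** In Study Procedures, question 6, item 3d, add the following:
- Before superimposition, an existing team member who does not measure relabels all models with arm-neutral codes. The same person removes one identical facial window, large enough to cover any of the four designs, from every pre-treatment, predicted and post-treatment lateral-incisor surface.
- One registration area and one measurement point, both outside that window, are defined for all teeth.
- An existing team member who sees only the cropped, recoded models performs the superimposition.

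In question 6, item 1, and in Data Confidentiality and Storage, question 9, drop attachment type from the participant code. Cropping without recoding would leave the arm readable from the file label, and recoding without cropping would leave it readable from any model that shows the attachment.

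This works whether attachments are on or off, and it can be applied to scans already taken. It needs no extra scan, visit or staff. The cost is a little software time per model and some loss of facial surface for matching. How far that loss affects registration has not been assessed, so the window should be no larger than the four designs require. No change to the timing of attachment removal is proposed.

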a. Routine clinical practice: All potential patients seeking orthodontic treatment will have an initial consultation appointment with the orthodontist. At this appointment, the orthodontist will have an opportunity to assess patient needs/ expectations as well as conduct an examination to present viable treatment options to the patient. All patients will also have their teeth and gums scanned by an intraoral scanner. This information is sent to Align Technology whose proprietary software (ClinCheck) is used to design and engineer a sequential set of trays that would progressively move teeth to their ideal positions in the mouth. ClinCheck software also provides the quantitative estimate of the magnitude of tooth movement required (in tenths of mm) as well as its direction (in degrees). Together, this information is used to design the clear aligners.

b. Study related screening:

During this consultation appointment, the patients will be evaluated to see if they meet the stated exclusion criteria (missing teeth in maxillary arch; lateral incisors with pathology/ restorations, treatment plan include extractions, presence of anterior cross bite, need for maxillary lateral incisor extrusion) to screen out ineligible study participants.

All patients who do not meet the exclusion criteria will be considered potential study participants and will be informed of the study and requested to participate and consent obtained. Their teeth and gums will be scanned as indicated under routine clinical care and the final inclusion will be determined based on the report generated by ClinCheck (>0.3mm lateral incisor extrusion and <6mm crowding). The time gap between intraoral scanning and generation of ClinCheck is a few days and getting the consent for all non-excluded participants is proposed out of respect for patient/ doctor's time because it precludes a need for a separate appointment (just to get consent) and improves efficiency.

It will be explained to the patient that they could be excluded from the study if analysis of ClinCheck software data indicates their ineligibility (required lateral incisor extrusion <0.3mm and crowding >6mm). Such patients would be considered screening failures.

5. * Does this study have a separate protocol document (i.e. a multisite or sponsor's protocol) that contains a detailed description of the study's methodology?

Yes

No

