The study is a 4-arm randomized trial. Subjects will be screened for eligibility based on inclusion/ exclusion criteria. Once informed consent is obtained, the participants will be randomly assigned to one of the four attachment designs. The biostatistician on the study team ([name]) will generate random sequence using a computer. The randomization will be in block of 4 and the list will be provided to the study team.

All study participants will be assigned a unique identifier (4 digit code) generated by the study team based on order of enrollment and whether they received horizontal, incisally bevelled, gingivally bevelled or optimized attachments. This key that links code to the patient will be stored in the PI's office computer that has restricted access (only to study personnel). The key will be destroyed when the all participants complete their second scan (data collection is complete).

All data records used for analysis will have this assigned code without any identifying information. This will minimize the amount of recontacting needed for children who turn 18 during data analysis stage.

ID: HM20021396

View: SF2 - Data Retention

Data Retention

1. * **Select all of the ways that individually identifiable information obtained during pre-screening and/or screening will be handled for individuals who DO NOT qualify for the study:**
 - Immediately destroy the information and identifiers (no data collected)
 - Immediately destroy the identifiers connected with the data (anonymization)
 - Store until the end of study & then destroy
 - Use as "screening failure" data by members of the study team
 - Provide to others outside of the research team (with the participant's permission)
 - Request permission from participant to maintain and use the identifiable information
 - Other
 - N/A - study does not require screening procedures**
2. * **Will participants be able to withdraw their data (paper, electronic, or specimens) from the study (e.g. ask that it be destroyed or returned) if they no longer wish to participate? (FDA-regulated studies should select No - see help text)**
 - Yes
 - No**
3. * **What will happen to the research materials (e.g. data, specimens, documents, etc.) when the research has been completed?**
 - Stored indefinitely with identifiers removed
 - Stored indefinitely with identifiers attached

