This is a short term study that will last a maximum of 6 months. In the unlikely situation that the participant enters adulthood at any stage of the study (while actively on the first series of aligners or during data analysis), we will re-consent him/her using the adult consent document. Even though the study itself lasts only 6 months, the comprehensive orthodontic treatment would take much longer (12-18 months). In a vast majority of cases, incisor correction is done at the start and we expect all data analysis to be completed within a few months after the second scan. There are 2 possibilities when the issue of re-consenting arise:

- a. If the participants turns 18 while they are still on aligner therapy (irrespective of whether they are on initial series or beyond): In these cases, the study team will have an opportunity to see the participant in person for routine follow-up and will re-consent in person
- b. In the rare instance where the patients are off aligner therapy when data analysis is still in progress, the study team will reach out to the participant over phone and will seek re-consenting. We have checked the box for waiver of documentation of re-consent.

ID: HM20021396

View: SF_IRB_StudyLocation_NonVCUSitesDetails

Non-VCU Site Details

1. * Name of institution or site:

[name] Orthodontics, [name]

2. * Provide a description of the institution's or site's role in the research and what study activities they will be performing:

[name] owns and runs the exclusive orthodontic practice in Richmond. He is also an adjunct faculty in the Department of Orthodontics at VCU SoD.

[name] will identify potential participants and recruit them in the study if the patient meets the inclusion/ exclusion criteria and sign the informed consent. He will inform the PI once the consent is obtained. The PI will then relay the randomized assignment of the attachment design to [name]. The patient will be treated in [name] office and all necessary data (intraoral scans and ClinCheck) will be shared with the PI through a HIPAA-secure portal maintained by Align Technology. All patient information (including demographic information and photos) are maintained in the cloud and can be accessed only by a Invisalign-registered doctor or staff. This access is restricted by an username and password.

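### Consent, not the ClinCheck report, is the written trigger for assigning the attachment, so a tooth can be allocated before its eligibility is known

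*Combined protocol and SAP*

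**What the plan says.** **Trigger for assignment.** Three places describe it.

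- Data Confidentiality and Storage, question 9: "Once informed consent is obtained, the participants will be randomly assigned to one of the four attachment designs". The sentence before this one has subjects screened on the inclusion and exclusion criteria.
- Non-VCU Site Details, question 2 (one private practice): the orthodontist will "recruit them in the study if the patient meets the inclusion/ exclusion criteria and sign the informed consent". Then: "He will inform the PI once the consent is obtained. The PI will then relay the randomized assignment of the attachment design".
- Study Procedures, question 6: team members send notice "when a study participant is recruited to the study through a secure email", and the person notified "will then communicate the randomly assigned attachment design to the treating orthodontist". The word *recruited* is not defined relative to ClinCheck.

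**Timing of eligibility.** Study Procedures, question 4, asks every patient not excluded at the consultation for consent. The teeth are scanned, and "the final inclusion will be determined based on the report generated by ClinCheck (>0.3mm lateral incisor extrusion and <6mm crowding"). The report takes a few days. Of patients who then prove ineligible it says: "Such patients would be considered screening failures". The withdrawal criteria (Risks, Discomforts, Potential Harms and Monitoring, question 5) also list ClinCheck ineligibility, described there as part of screening.

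**Unit.** Study Procedures, question 6, randomises the individual lateral incisor. Study Population, question 4, makes the extrusion criterion depend on ClinCheck. Compensation, question 1, confirms that one or both of a patient's lateral incisors may qualify.

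**The concern.** Eligibility should be settled while the arm is unknown. If consent alone releases the assignment, the treating orthodontist can know the arm before the report that decides inclusion exists. Three things then follow. Assignments are used up by teeth that never enter the trial. The blocks of 4 no longer guarantee equal arms. A borderline eligibility call can be made with the arm in view.

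Tooth-level randomisation sharpens the problem. At consent it is not yet known whether a patient needs no assignment, one or two.

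Most ClinCheck exclusions are numeric and leave little room for judgement. The room that remains is at the boundaries, where the documents disagree with themselves. For extrusion this can arise in practice, since "ClinCheck software also provides the quantitative estimate of the magnitude of tooth movement required (in tenths of mm"), so a value of exactly 0.3 mm can occur.

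**Working it through.** **1. Order of events, side by side**

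| Step | Where stated | Relation to ClinCheck |
|---|---|---|
| Consent sought | Study Procedures, q. 4: at the consultation | Before the report |
| Scan, then report | Study Procedures, q. 4: a few days apart | – |
| Final inclusion | Study Procedures, q. 4 | On the report |
| Assignment | Data Confidentiality and Storage, q. 9: on consent | Not tied to it |
| Assignment relayed | Non-VCU Site Details, q. 2: on consent | Not tied to it |
| Assignment relayed | Study Procedures, q. 6: on recruitment | Undefined |

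No supplied section holds the assignment until the report.

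**2. Boundary wording**

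| Value | Treated as eligible, or not excluded | Treated as not meeting inclusion |
|---|---|---|
| Extrusion exactly 0.3 mm | Study Population, q. 4 (0.3 mm or more) and q. 5 (excludes less than 0.3 mm); Study Procedures, q. 4 (ineligible if below 0.3 mm) | Study Procedures, q. 4, and Secondary Data/Specimen Details, q. 1 (inclusion above 0.3 mm) |
| Crowding exactly 6 mm | Study Procedures, q. 4 (ineligible only above 6 mm) | Study Population, q. 4, and Study Procedures, q. 4 (inclusion below 6 mm) |

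Study Procedures, question 4, falls in both columns on both rows.

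**3. Size of the effect on balance**

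Inputs from Study Procedures, question 6: 80 teeth, four arms, blocks of 4. So 80/4 = 20 teeth per arm, in 80/4 = 20 blocks. The documents give no ClinCheck failure rate, so p = 10%, 20% and 30% are assumed, with failure unrelated to arm. Two cases bracket the dependence between a patient's teeth:

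- Teeth fail independently: expected complete blocks = 20 × (1 − p)^4.
- 40 patients with two teeth each, both failing together (two patients per block): expected complete blocks = 20 × (1 − p)^2.

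| p | Complete blocks, independent | Complete blocks, paired | Mean gap, independent | Mean gap, paired |
|---|---|---|---|---|
| 10% | 20 × 0.6561 = 13.1 | 20 × 0.81 = 16.2 | 2.7 teeth | 2.1 teeth |
| 20% | 20 × 0.4096 = 8.2 | 20 × 0.64 = 12.8 | 3.6 teeth | 2.9 teeth |
| 30% | 20 × 0.2401 = 4.8 | 20 × 0.49 = 9.8 | 4.2 teeth | 3.4 teeth |

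The gap is the largest arm minus the smallest, averaged over simulated trials (400,000 independent, 40,000 paired). With release after ClinCheck, all 20 blocks are complete at this stage and the gap is 0.

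The imbalance alone costs little precision. Compared with equal arms of the same total, mean efficiency (harmonic mean of the arm sizes divided by their arithmetic mean) is about 98% to 99.7% across these six cases.

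**The case against.** The strongest reply is that release after ClinCheck is what the team means. The consent-trigger sentence answers a form question about coding subject identifiers, and the sentence before it names screening. The private practice recruits a patient who meets the criteria, and one of those criteria is read from ClinCheck. Patients who fail on the report are called screening failures, which is pre-randomisation language. Consent Groups, question 8, allows two weeks to decide, so some consents could follow the report. And if nobody knows which teeth qualify before ClinCheck, tooth assignments could hardly be issued earlier.

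Much of this stands, and it makes later release a plausible intention. It does not settle the order. Children, question 3, and Consent Groups, question 6, use the same inclusion and exclusion criteria for a judgement made at the consultation or at the start of the consent process. Under the Study Procedures sequence the report does not yet exist at that point. So a reference to meeting the criteria does not show that ClinCheck has been seen.

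It is also fair that the loss of balance is small, that the consultation already screens for need of lateral incisor extrusion, and that the target of at least 20 teeth per group leaves room for replacement. Replacement restores numbers. It does not undo an exclusion made with the arm known.

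**Conclusion.** The point holds as a gap in the written sequence. Two sections tie assignment to consent, a third uses an undefined trigger, and none makes it wait for the report that decides eligibility. Following the text permits exclusion after allocation with the arm known to the treating orthodontist.

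A reader might infer that the trial will in fact allocate before eligibility is known. The documents do not show that, because their screening language is compatible with later release.

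A reader might also infer that the comparison of attachments will be biased. That is not supported either. If exclusion is unrelated to arm the expected bias is 0, and no section says who makes the ClinCheck eligibility call or whether its values can be revised. The documents allow no other figure for bias.

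What can be sized is balance: about 5 to 16 of 20 blocks complete and a mean gap of about 2 to 4 teeth, resting on assumed failure rates of 10% to 30%, unrelated to arm and without replacement. The point does not extend to later withdrawals for poor compliance, which do not depend on when the assignment is released.

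**What to change.** - Amend Study Procedures, question 6; Data Confidentiality and Storage, question 9; and Non-VCU Site Details, question 2, so that all give one order: consent, scan, ClinCheck eligibility recorded for each tooth, then release of that tooth's assignment. Consent can stay at the consultation, as Study Procedures, question 4, wants.
- In the withdrawal criteria, describe ClinCheck ineligibility as a screening failure before randomisation.
- Before any assignment is released, reconcile the passages on extrusion of exactly 0.3 mm and crowding of exactly 6 mm, so that each value has one stated status.

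The cost is protocol wording and a few days' wait for a report that routine care already produces, with no extra visit. If the attachment has to be specified with the first ClinCheck submission, which the documents do not say, the ClinCheck plan would need a revision after release.
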